Pioglitazone for Idiopathic Gastroparesis NCT04300127 8/24/2020

Clinical Protocol Synopsis- Pioglitazone for the Treatment of Gastroparesis

Title

Pioglitazone for the Treatment of Idiopathic Gastroparesis (PIOGAS Study)

Type of study

• Open label pilot study

Objective

- The principal objective of this pilot study will be to evaluate whether 8 weeks of treatment of pioglitazone will improve symptoms as measured by the Gastrointestinal Symptom Index Daily Diary (GCSI-DD) in patients with Idiopathic Gastroparesis
- Secondary objectives of this study include:
 - To determine the effects of pioglitazone on other symptoms associated with gastroparesis using the Patient Assessment of Upper Gastrointestinal Symptom Severity Index (PAGI-SYM) and the Gastrointestinal Symptom Rating Scale (GSRS),
 - To determine the effects of pioglitazone on gastric emptying as measured by the ¹³C- Spirulina breath test,
 - To determine the effects of pioglitazone on satiety as measured by a liquid caloric test
 - To determine the effects of pioglitazone on depression and anxiety using the Beck Depression Inventory and State-Trait Anxiety Scores,
 - To determine the effects of pioglitazone on Quality of Life using the PAGI-QoL and SF-36 questionnaire,
 - To determine the effects of pioglitazone on markers of inflammation (CRP and ESR) and serum cytokine levels
 - And to determine the nature and incidence of adverse effects from a 12-week course of pioglitazone.

Treatment group

• Pioglitazone (30 mg po qd)

Population

 Age 18 years or older at registration with nausea, vomiting, and other symptoms suggestive of patients with chronic nausea and vomiting of presumed gastric origin, with symptomatic gastroparesis.

Study duration

- Up to 4 weeks of screening prior to pioglitazone treatment
- 8 weeks of treatment starting at initial dose of pioglitazone
- **4 weeks** of washout period
- Length of recruitment: 16 months

Sample size justification

- Total of **20 patients**
- Primary comparison: Baseline PAGI-SYM score versus 4, 8, and 12 weeks.

Number of clinical centers

- Johns Hopkins Bayview Medical Center.
- Mayo Clinic Scottsdale, Arizona This site will not perform enrollment of patients, It will only intervene as data analysis center under the supervision of [name].
- •

Inclusion criteria

- Age 18 years or older at registration

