- Diagnosis of gastroparesis as documented by gastric emptying scintigraphy (4-hour emptying after a low-fat meal with any combination of 2 and 4 hour retention of >60% and 10% respectively)
- Ongoing symptoms referable to gastroparesis (i.e. nausea and vomiting, bloating, and abdominal pain)
- Exclusion of other causes of symptoms such as mechanical gastrointestinal obstruction, uncontrolled esophagitis, peptic ulcer disease, etc. by standard radiographic or endoscopic tests
- Females will be required to use adequate contraceptive methods during study participation as determined by the Principal Investigator and the study team members

Exclusion criteria

- Another active disorder which could explain symptoms in the opinion of the investigator
- Age < than 18 years
- Pregnancy or nursing
- Previous surgery of the upper gastrointestinal tract including vagotomy
- Another active disorder which could explain symptoms in the opinion of the investigator
- Use of narcotics more than 3 days per week
- Significant hepatic injury as defined by significant alanine aminotransferase (ALT) and aspartate aminotransferase (AST) elevations of greater than 2xULN or a Child-Pugh score of 10 or greater
- Serious systemic disease, such as recent myocardial infarction/unstable angina, decompensated congestive heart failure, severe pulmonary disease with dyspnea at rest, or altered mental status from any cause
- Diabetes as defined by HbA1c >6.5 and/or fasting blood sugar of >125 mg/dL
- Contraindications to pioglitazone such as hypersensitivity or allergy
- Concurrent use of: estradiol, ethynyl estradiol, mestranol, pazopanib, warfarin, digoxin, atorvastatin, ranitidine, gemfibrozil, fexofenadine, midazolam
- Any other condition, which in the opinion of the investigator would impede compliance or hinder completion of the study
- History of bladder cancer or family history of bladder cancer
- Failure to give informed consent

Outcome measures

- **Primary:** The primary outcome measure is a binary (0,1) variable indicating improvement as measured by a decline of 1 or more in the total GCSI score
- Secondary outcome measures will be defined to address the following areas:
 - (1) Gastrointestinal symptoms
 - Subscores for the GCSI: nausea/vomiting, postprandial fullness, bloating
 - Total and Subscores for the GSRS
 NIH Patient Reported Outcome Measurement Information System (PROMIS)

gastrointestinal symptom scales.

- (2) Quality of Life
 - PAGI-QoL
 - SF-36

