- (3) Inflammatory Markers
 - CRP and ESR
- (4) Mood and Behavior
 - Beck Depression Inventory
 - State-Trait Anxiety
- (5) Adverse Events
 - Biochemical tests
 - Symptoms of cardiac or pulmonary disease
 - Any other AE reported or noted throughout the study and follow-up

Justification of sample size

This will be a pilot study recruiting 20 candidates.

Statistical analysis

All analyses will be on an intention-to-treat basis. Patients who do not have any of the decline of 1 or more in the total GCSI score recorded during the period of treatment will be counted as not improved (i.e., 0) for the primary outcome. Comparisons will also be made with baseline total GCSI score and other secondary outcomes. Numerical changes will be analyzed by descriptively comparing the between-treatment group differences in mean and median changes; P-values will be derived from Wilcoxon rank sum tests for comparison of the distribution of changes in each group The two-sided P-values so derived will be reported in the primary results paper of the trial. A two-sided P-value of 0.05 will be considered statistically significant.

Standard treatment recommendations

During the screening period, patients will receive a standardized set of recommendations to include dietary modification. The patient's medications are reviewed to eliminate drugs that might exacerbate the underlying dysmotility disorder or prevent the beneficial actions of a prokinetic agent. Dietary modification and use of pain medications as appropriate are the primary management approaches. If symptoms require further treatment during the trial, patients will be instructed to take rescue medications that they would usually take such as prochlorperazine for nausea and vomiting, and tramadol for abdominal pain. These recommendations have been prepared by the GpCRC Steering Committee as standard of care in the management of patients with gastroparesis or related disorders. This will help ensure that the patients in both treatment groups receive standard of care treatment.

Visit schedule

- Screening: at least 1 visit separated by at least 1 calendar day prior pioglitazone treatment; screening period can last no more than 4 weeks after registration
- Final pre-treatment interview, dispensing of study agent
- Follow-up visits: every 4 weeks after pioglitazone treatment throughout the 12 week study
- Post-treatment: follow-up at **16 weeks**

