Week 4 visit: Medical history including clinical global patient impression (GCPI) questionnaire. The following questionnaires should be completed: Patient Assessment of Upper Gastrointestinal Disorders Symptom Severity (PAGI-SYM), NIH Patient Reported Outcome Measurement Information System (PROMIS) gastrointestinal symptom scales. Review study drug adherence and tolerance of the study drug with the participant. The daily GCSI-DD completed by the patient each night since beginning treatment will be collected by the clinical center staff.

In addition the patient will be provided 4 weeks of GCSI-DD for completion each night before bed.

- Week 8 visit: Medical history including clinical global patient impression (GCPI) • questionnaire. The following questionnaires should be completed: Patient Assessment of Upper Gastrointestinal Disorders Symptom Severity (PAGI-SYM), NIH Patient Reported Outcome Measurement Information System (PROMIS) gastrointestinal symptom scales. Review study drug adherence and tolerance of the study drug with the participant. The GCSI-DD completed by the patient each night since the last visit will be collected by the clinical center staff. In addition the patient will be provided 4 weeks GCSI-DD for completion each night before bed. Laboratory test results that need to be recorded from chart review or obtained as part of screening include: CBC (complete blood count), metabolic panel (sodium, potassium, chloride, bicarbonate, calcium, BUN, creatinine, alanine aminotransferase (ALT), aspartate aminotransferase (AST), magnesium, albumin, total protein). CRP and ESR
- Week 12 visit: Medical history, physical exam including clinical global patient impression (GCPI) questionnaire. The following questionnaires should be completed: Patient Assessment of Upper Gastrointestinal Disorders Symptom Severity (PAGI-SYM), Gastrointestinal Symptom Rating Scale (GSRS), Health Survey (SF-36v2), Beck Depression Inventory (BDI-II), and State Trait Anxiety Inventory (STAI), NIH Patient Reported Outcome Measurement Information System (PROMIS) gastrointestinal symptom scales. Review study drug adherence and tolerance of the study drug with the participant. The GCSI-DD completed by each the patient night since the last visit.

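### The primary responder outcome has no assessment time or window, so as worded one qualifying score at any point in treatment counts as improved, which overstates response relative to the 8-week objective

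*Combined protocol and SAP*

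**What the plan says.** All places are in the combined protocol and SAP.

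- **Outcome measures:** "The primary outcome measure is a binary (0,1) variable indicating improvement as measured by a decline of 1 or more in the total GCSI score". No visit, averaging window or confirmation is given.
- **Statistical analysis:** the value 0 goes to "Patients who do not have any of the decline of 1 or more in the total GCSI score recorded during the period of treatment". This is the only sentence that turns the outcome into a scoring rule.
- **Objective:** the question is "whether 8 weeks of treatment of pioglitazone will improve symptoms as measured by the Gastrointestinal Symptom Index Daily Diary (GCSI-DD").
- **Follow-up visits, week 8:** "The GCSI-DD completed by the patient each night since the last visit will be collected by the clinical center staff". The screening visit supplies one week of nightly diaries before treatment.
- **Sample size justification:** the primary comparison line names a different instrument, the PAGI-SYM, at weeks 4, 8 and 12 against baseline. The questionnaire descriptions say that the GCSI is contained in the PAGI-SYM, with items scored 0 to 5. They do not say whether the total is an item mean or a sum.
- **Type of study and Treatment group:** "Open label pilot study", with one treatment group and no control.
- **Treatment length:** 8 weeks under Study duration, but a 12-week course in the adverse-effects objective.

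**The concern.** The objective asks about the effect of 8 weeks of treatment. The scoring sentence asks whether a fall of at least 1 point was ever recorded while on treatment. These are different quantities. Under the second, one good night in week 2 counts the same as sustained benefit, and each additional score is another chance to qualify.

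A control arm would show how often such crossings happen without drug, but there is none and the plan sets no reference response rate. Dietary advice in screening and rescue medication during the trial can also move symptoms. A high response proportion could therefore not be interpreted, yet it is the figure on which a later trial would build.

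**Working it through.** **Nothing to reproduce.** The plan gives N = 20 without an effect size, SD, power or null response rate.

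**Direction, without assumptions about variability.** The minimum of a set of scores is never above their mean. If the week 8 seven-night mean is at least 1 below baseline, at least one of those nights is too. Every week 8 responder is therefore also an any-night responder, and the any-night proportion can only be equal or higher. The same holds for best of two visits against the week 8 visit alone.

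**Inputs for the size**

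- From the documents: nightly diary; 7 baseline nights; 8 weeks × 7 = 56 treatment nights; visits at weeks 4 and 8; threshold 1 point; items scored 0–5.
- Diary supply: three weeks are provided at treatment start and four more at week 4, which can be read as 7 × 7 = 49 nights.
- Assumed, because the documents give no figures: total scored as the 0–5 item mean; true mean about 3; within-patient nightly SD 0.3 to 0.8; night-to-night correlation 0.3 to 0.7; no drug effect.

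**Diary.** First-order autoregressive scores were simulated for 40,000 patients per setting and clipped to 0–5. The comparison is P(lowest of 56 nights ≤ baseline mean − 1) against P(week 8 seven-night mean ≤ baseline mean − 1).

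| Nightly SD | Any of 56 nights | Week 8 mean |
|---|---|---|
| 0.3 | 6–8% | under 0.1% |
| 0.4 | 32–35% | 0–1% |
| 0.5 | 53–64% | 0–3% |
| 0.8 | 83–94% | 3–11% |

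Using 49 nights lowers the middle column by about 1 to 4 points. Hand check at SD 0.5, with independent nights and a baseline known without error: 1 − Φ(1/0.5)^56 = 1 − 0.97725^56 ≈ 0.72. The simulation with independent nights and an estimated baseline, without clipping, gives 0.685.

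**Visit scores.** One baseline score and independent errors. For one visit, P = Φ(−1/(SD × √2)):

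- SD 0.5: Φ(−1.414) = 7.9%; best of two visits, simulated, 13%
- SD 0.6: Φ(−1.179) = 11.9%; best of two, 20%
- SD 0.7: Φ(−1.010) = 15.6%; best of two, 25%

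If treatment runs 12 weeks, best of three visits gives 18%, 25% and 32%.

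**Scale.** If the total is a sum (9 items, 0–45), a 1-point fall is 1/9 = 0.11 on the mean scale. Best of two visits then gives 56–62% with no drug effect (SD 0.3–0.7 on the mean scale).

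**Share of responses that would occur anyway.** This is the rate with no effect divided by the rate under an assumed true fall of 0.5.

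- Any diary night, correlation 0.5: 7/77 ≈ 10% at SD 0.3; 35/90 ≈ 39% at 0.4; 61/95 = 64% at 0.5; 85/98 = 87% at 0.7.
- Best of two visits: 13/37 ≈ 36% at SD 0.5; 20/41 ≈ 48% at 0.6; 25/45 = 56% at 0.7.

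**Precision.** With 10 of 20 responders, the exact 95% interval is 27% to 73%. The no-effect rate of 53–64% at nightly SD 0.5 lies inside it.

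**The case against.** **The sentence is garbled and may be a missing-data rule.** It follows directly after the intention-to-treat statement and says only who is scored 0. It never says in terms that one night is enough for a 1. This stands as a possible intention. It does not close the gap, because the positive definition under Outcome measures has no time point and no other section supplies one.

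**The score may come from visits, not nights.** The primary comparison line names the PAGI-SYM, so there may be only two on-treatment scores in 8 weeks. This also stands. On that reading, fixing the time point lowers the no-effect rate only from 13–25% to 8–16%.

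**A reader might infer that most recorded responses would be fluctuation.** The documents do not support that. They give no within-patient SD. With an assumed true fall of 0.5, fluctuation makes up most of the responses only at a nightly SD of about 0.5 or more, or about 0.7 for best of two visits. At a nightly SD of 0.3 it is about a tenth.

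**A reader might also infer that the rule can produce a false significant result.** The plan does state that "A two-sided P-value of 0.05 will be considered statistically significant", but the test it names is a rank sum test on numerical changes. No test or success threshold is attached to the responder proportion. Planned mean and median changes also give some view of overall benefit.

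**It is a pilot.** "This will be a pilot study recruiting 20 candidates" is the whole sample size justification. This limits the harm but does not make the proportion answer the stated question.

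**Conclusion.** The point holds in this form: the primary outcome has no assessment time or window, and as worded one qualifying score during treatment counts as improved. Relative to improvement after 8 weeks the response proportion is biased upward, and there is no control against which to judge it. The direction follows from the rule itself.

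The size cannot be fixed from the documents. It ranges from a few percentage points (nightly SD 0.3) to most patients qualifying with no drug effect (SD 0.5 and above), and is smaller if only visit scores count. These figures assume a 0–5 mean scale, a constant patient mean and the correlations listed. This should be fixed. It falls short of a critical defect because this is a 20-patient pilot with no decision rule on the proportion.

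**What to change.** Under Outcome measures and Statistical analysis, define a patient as improved (1) if the mean GCSI-DD total, scored as the 0–5 item mean, over the last 7 diary nights before the week 8 visit is at least 1 point below the mean of the 7 baseline nights, and 0 otherwise. Count patients without week 8 diary data as 0, and state how many completed nights are needed for the mean to be used. Report the any-time proportion as descriptive only.

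Reconcile two other places with this definition: the primary comparison line naming the PAGI-SYM at weeks 4, 8 and 12, and the 8-week and 12-week statements of treatment length, which determine what the period of treatment means. Week 8 is proposed here as the assessment time that the objective implies, not as a view on how long treatment should last.

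The cost is a few sentences and no new data, since the baseline week and the four weeks up to week 8 are already collected nightly. The reported response rate will be lower. Patients with an early fall who then leave change from 1 to 0, which alters the current wording and should be stated openly. The change does not replace a control or a pre-set reference response rate.

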As part of the screening process for the PIOGAS trial, the patient must have a standardized 4-hour scintigraphic evaluation of gastric emptying using a low fat Egg Beaters meal that is available for review by the study physician. The standard of care gastric emptying scintigraphy may have been obtained at any time within 2 years prior to the registration date. Patients must also have a normal upper endoscopy within the last 2 years, to rule out other potential causes of symptoms such as mechanical obstruction, inflammatory or other structural lesions of the GI tract or non-gastrointestinal causes. Recording of screening data on trial forms may not start until the patient has signed the PIOGAS trial consent statement. Screening and baseline data collection procedures will include questionnaires, physical examination, various laboratory tests, clinical procedures on patients, and review of the patient's medical chart. Data abstracted from a patient's chart may include laboratory, endoscopy, scintigraphy, and radiology test results. Prior therapy will be reviewed and patients will be asked to stop specific treatments such as antiemetic medications. Baseline and follow up questionnaires can be answered through REDcap.

All participants who sign the consent statement will be registered in the trial database (REDcap). Each participant who starts screening will be accounted for at the end of screening, as either a screening success or a screening failure. A screening failure is defined and a participant who signed the consent form and was registered for the PIOGAS trial data system, but is found to be ineligible prior to start of treatment; screening failures include patients who meet medical eligibility criteria but change their mind and do not consent to participation in the trial. The reason for screening failure will be recorded and keyed in the trial database.

Screening visit: The patient should be in a fasting state (no food or drink after midnight the night before) for this visit. The patient will sign the consent form at or prior to the screening visit and will undergo a history and physical examination to identify other illness and contraindications for participation such as use of antiemetic medications.

In addition, the patient will be provided one week supplies of the Gastroparesis Cardinal Symptom index-Daily Diary (GCSI-DD) for completion each night before bed.

The patient will complete the following questionnaires:

- PAGI-SYM

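### The P-value rule needs a second group that this single-arm study lacks, and a baseline test in its place would not control error for a pioglitazone effect

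*Combined protocol and SAP*

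**What the plan says.** The combined protocol and SAP describes an "Open label pilot study" with a single entry under Treatment group. On size it says only "This will be a pilot study recruiting 20 candidates".

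The objectives are worded as drug effects. The principal one is to "evaluate whether 8 weeks of treatment of pioglitazone will improve symptoms"; the first secondary one reads "To determine the effects of pioglitazone on other symptoms associated with gastroparesis".

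Baseline is the only comparator. Sample size justification gives the primary comparison as baseline PAGI-SYM against weeks 4, 8 and 12. Outcome measures makes the primary outcome a yes/no response (a fall of at least 1 point in total GCSI) and gives no reference rate. Statistical analysis adds: "Comparisons will also be made with baseline total GCSI score and other secondary outcomes". None of these places names a test.

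The only P-value rule is in Statistical analysis. It describes differences between treatment groups, derives P-values from Wilcoxon rank sum tests on the changes in each group, sends them to the primary results paper, and ends: "A two-sided P-value of 0.05 will be considered statistically significant". Standard treatment recommendations also speaks of two treatment groups.

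**The concern.** There are two linked problems. First, the test that supplies the P-values compares two groups, and the study has one. Second, the natural repair, a paired or one-sample test against baseline, answers a different question from the objectives. Its null hypothesis is no change. A patient's score can change without any drug effect, and several routes are visible in the protocol:

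- Dietary advice and a medication review take place during screening, and usual rescue medication is allowed during the trial (Standard treatment recommendations).
- Symptoms are self-reported and treatment is unblinded, so expectation can act.
- Entry requires ongoing symptoms (Inclusion criteria), so some regression to the mean is possible.
- PAGI-SYM is completed at screening and is not listed again at treatment start (PIOGAS Study Data Collection Schedule). Effects of pre-dose changes in diet or medication can therefore enter the change from baseline.

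Nothing in the plan warns that a P-value against baseline cannot separate these from pioglitazone. With a declared threshold and causal objectives, a significant change would be reported as a drug effect.

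**Working it through.** **Inputs.** From the documents: one group (Treatment group); n = 20 (Sample size justification); two-sided 0.05 (Statistical analysis). Not in the documents: the SD of change, any non-drug mean change, a response rate without the drug, power, or dropout. So n = 20 has no derivation to reproduce, and every value of d and p below is an assumption.

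**Step 1: the test as written.** The rank sum statistic is the sum of one group's ranks in the pooled sample. With 20 patients in one group and none in the other it is always 1 + 2 + ... + 20 = 20 × 21 / 2 = 210. It cannot vary, so there is no P-value.

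**Step 2: what 5% means after the repair.** For a signed-rank test at n = 20, reject if W ≤ 52 or W ≥ 158 (210 − 52 = 158). With no change from baseline the exact size is 0.0484; the next larger rejection region has size 0.0532, above 0.05. The plan's level is therefore right for the null of no change.

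**Step 3: what 5% means for an inert drug.** Write mean change = drug part + non-drug part, and set the drug part to zero. Let d = non-drug mean improvement / SD of change. For the paired t-test:

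- noncentrality λ = d × √20 = 4.472 d
- critical value t(0.975, 19 df) = 2.093
- P(significant) = P(|T| > 2.093), with T noncentral t on 19 df

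The signed-rank column is from 40,000 simulated normal samples, except the first row, which is the exact size.

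| Assumed d | λ | t-test, two-sided | t-test, favourable direction | Signed-rank, two-sided |
|---|---|---|---|---|
| 0 | 0 | 5.0% | 2.5% | 4.8% |
| 0.1 | 0.447 | 7.1% | 6.2% | 6.9% |
| 0.2 | 0.894 | 13.6% | 13.3% | 13.0% |
| 0.3 | 1.342 | 24.7% | 24.6% | 23.6% |
| 0.4 | 1.789 | 39.7% | 39.7% | 38.2% |
| 0.5 | 2.236 | 56.5% | 56.4% | 54.6% |

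**Step 4: the binary primary outcome.** With no drug effect and response rate p without the drug, P(6 or more of 20) = Σ C(20,k) p^k (1 − p)^(20−k) over k = 6 to 20. This is 1.1%, 19.6%, 58.4% and 87.4% for assumed p of 10%, 20%, 30% and 40%. Six is used because at p = 10% it is the smallest count whose upper tail is at most 2.5% (five gives 4.3%). The same result would be surprising or ordinary depending on a rate that the plan does not state.

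**The case against.** The strongest reply is that a pilot may be uncontrolled, that the plan says so, and that it calls the numeric comparisons descriptive. That stands, and it limits the weight of the point. The criticism is of the significance rule and the causal wording, both of which the plan chose, and not of the design.

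A second reply is that the direction of non-drug change is not settled. Patients are asked at screening to stop treatments such as antiemetics, which could raise scores. Part of any dietary benefit may already be in the baseline diary. No minimum GCSI score is required, so regression to the mean may be weak. Expectation is a less obvious influence on CRP and ESR. All of this stands. Non-drug worsening would hide a benefit rather than imitate one; either way the baseline test does not isolate the drug.

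Three stronger readings are tempting but not supported:

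- *That the plan specifies a test of change against zero.* It does not. The baseline sentence names no test, and the test it does name is between groups.
- *That significance is likely for an inert drug.* With an assumed non-drug improvement of 0.3, 0.5 or 0.7 points and an SD of 0.9, 1.1 or 1.3, the same formula gives 16% to 91% in the favourable direction. Five of those nine combinations are below 50% (16.4%, 21.1%, 29.3%, 37.2% and 48.8%), and all inputs are assumed.
- *That no off-drug data will exist.* Study duration lists a 4-week washout after 8 weeks of treatment, and the diary is collected to week 12. What is missing is an estimate of untreated change before dosing. The washout data are themselves hard to place, because the documents conflict on duration: a secondary objective refers to a 12-week course, the week 12 visit reviews drug adherence, and Visit schedule puts post-treatment follow-up at 16 weeks.

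**Conclusion.** The point holds in this form. The rank sum rule cannot be applied to one group; that follows from the documents alone. Any paired or one-sample replacement has a 5% error rate for no change from baseline, and that is not the error rate for the claim that pioglitazone improves symptoms. How far the two differ cannot be derived from the documents. As an illustration, a non-drug improvement of 0.1 to 0.5 SD, with n = 20, normally distributed changes and complete data, makes a two-sided 0.05 paired t-test significant for an inert drug in about 7% to 57% of studies. The binary outcome has the same gap because it has no reference rate. The plan should be corrected before analysis; the design need not change for a pilot.

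**What to change.** In Statistical analysis:

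1. Delete the rank sum test, the references to differences between treatment groups, and the sentence setting 0.05 as significant. Reword the sentence on P-values in the primary paper, which depends on the deleted test.
2. Report the responder proportion with an exact 95% confidence interval, and numeric changes from baseline with 95% confidence intervals.
3. If a P-value is wanted, take it from a signed-rank test and label it as testing change from baseline only.
4. State that these results describe change during treatment and do not establish a pioglitazone effect.

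Reword the principal and secondary objectives to change during treatment, and remove the mention of two treatment groups from Standard treatment recommendations.

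These are text edits. The cost is that the pilot can no longer claim a statistically significant drug effect.

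A longer pre-dose diary is not recommended as a remedy. It could not capture expectation that begins with dosing, it would be confounded by stopping antiemetics and by dietary advice, and it would lengthen screening. Before any off-drug diary data are interpreted, the statements on treatment and washout duration in Objective, Study duration, Visit schedule and Follow-up visits must be reconciled.

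### The only named test compares treatment groups in a one-group study, so it cannot be run, and the source and week of the primary outcome are not fixed

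*Combined protocol and SAP*

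**What the plan says.** **Design.** The synopsis describes an open-label pilot of 20 patients. Under the heading "Treatment group" it lists pioglitazone only. No section describes a control, a placebo or randomisation.

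**Test.** The Statistical analysis section describes numerical changes by contrasting treatment groups and states that "P-values will be derived from Wilcoxon rank sum tests for comparison of the distribution of changes in each group". These two-sided P-values are to go into the primary results paper and be judged at 0.05. Standard treatment recommendations also speaks of two treatment groups. Comparison with the baseline GCSI is mentioned, without a method.

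**Primary outcome.** Its source and time are described in different ways:
- Objective: to "evaluate whether 8 weeks of treatment of pioglitazone will improve symptoms as measured by the Gastrointestinal Symptom Index Daily Diary (GCSI-DD").
- Sample size justification: "Primary comparison: Baseline PAGI-SYM score versus 4, 8, and 12 weeks". The Objective section lists PAGI-SYM as secondary.
- Outcome measures: a binary "variable indicating improvement as measured by a decline of 1 or more in the total GCSI score", with no source or week. The PAGI-SYM description under Specific Tests and Questionnaires says that the GCSI is part of that questionnaire, so diary and questionnaire are both candidates.
- Statistical analysis: patients without such a decline recorded while on treatment count as not improved.

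**Treatment length.** Study duration gives 8 weeks "of treatment starting at initial dose of pioglitazone" and 4 weeks "of washout period". The last secondary objective refers to the "nature and incidence of adverse effects from a 12-week course of pioglitazone". The Visit schedule places the post-treatment follow-up at week 16.

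**The concern.** A rank-sum test compares two independent samples, and this study has one. The plan commits to P-values and a significance level but gives no procedure that can produce them. If nothing is fixed beforehand, the analyst has to choose a test, an instrument and a week, and may do so after seeing the data.

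The time rule also affects the primary result directly. A responder outcome that can be met on any of several occasions gives a higher proportion than one met at a single week, even when nothing has changed. With no comparator, no second arm shares that upward shift, so it goes straight into the reported figure.

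**Working it through.** **The plan's own figure.** The only figure is N = 20. The documents give no effect size, SD, reference response rate or power, so there is nothing to reproduce. The size is stated as a pilot size, and no power claim is contradicted.

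**1. Can the named test be run?** The rank-sum statistic counts pairs with one member from each group, so it lies between 0 and n1 × n2. With n1 = 20 and n2 = 0 there are 20 × 0 = 0 pairs. Run on 20 changes against an empty group, the software returned no statistic and no P-value.

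**2. Could it be used on baseline against follow-up scores?** It would run, but it ignores the pairing. In a simulation with 20 patients, normal scores and 5,000 runs, the correlations being assumed:

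| Baseline/follow-up correlation | Actual type I error (nominal 5%) | Rank-sum power at a change of 0.7 SD of change |
|---|---|---|
| 0.3 | 2.0% | 73% |
| 0.5 | 0.8% | 59% |
| 0.7 | 0.2% | 30% |

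The signed-rank test has about 82% power at the same change.

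**3. How much does the time rule matter?** Assumptions: no true mean change; normal changes with SD s = 0.7 to 1.0 points; equal correlation r = 0.5 to 0.9 between times; total GCSI on a 0 to 5 scale. The documents score PAGI-SYM items 0 to 5 but do not say how the total is formed.

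- One fixed week: P = Φ(−1/s). For s = 0.7, Φ(−1.43) = 7.7%. For s = 1.0, Φ(−1) = 15.9%.
- Any of k times: P = 1 − ∫ φ(u) [1 − Φ((−1/s − u√r)/√(1−r))]^k du.

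Diary weeks supplied by week 8: three after the first dose (Treatment Start Visit, reading its misspelt number as three) plus four at the week 4 visit, 3 + 4 = 7.

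| Rule | s = 0.7, r = 0.9 | s = 1.0, r = 0.5 |
|---|---|---|
| One fixed week | 7.7% | 15.9% |
| Week 4 or week 8 (k = 2) | 10.2% | 25.5% |
| Any of seven diary weeks (k = 7) | 15.1% | 47.6% |

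In the last column, the expected number of chance responders among 20 rises from 20 × 0.159 = 3.2 to 20 × 0.476 = 9.5.

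**4. What precision does the proportion have?** The exact 95% limits for x of n are the 2.5% point of Beta(x, n−x+1) and the 97.5% point of Beta(x+1, n−x). For 10/20, Beta(10, 11) gives 27.2% and Beta(11, 10) gives 72.8%. Likewise 5/20 gives 8.7% to 49.1%, 8/20 gives 19.1% to 63.9%, and 12/20 gives 36.1% to 80.9%.

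**5. What would a within-patient analysis give?** At n = 20 the signed-rank 95% interval, built from averages of pairs of changes (exact critical value 52), has a mean half-width of 0.474 SD of the change and coverage of 95.1% in 20,000 simulated runs with normal changes. It is an interval for the Hodges-Lehmann estimate, which equals the median only if changes are symmetric.

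**The case against.** The strongest reply is that the faulty sentence does not govern the primary outcome. It covers numerical changes. The outcome labelled primary is binary, with an intention-to-treat basis and a default of not improved. This is a pilot without a power claim, and comparison with baseline is clearly intended. That stands, and it limits the point: a reader might infer that the trial has no usable primary result, but the proportion can be computed once source and week are known. It does not rescue the P-values promised for the primary paper.

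A reader might also count four rival primary definitions. The documents do not support that: Outcome measures and Statistical analysis describe the same binary outcome, the latter adding a time window and a default.

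Nor do the documents settle that a decline at any time on treatment counts. The sentence is garbled and can equally mean that patients with nothing recorded count as not improved. No section scores weekly diary means. The seven-week figures therefore show what is possible under one reading, not what is planned.

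Finally, a reader might infer an inflated false-positive rate from testing weeks 4, 8 and 12 separately. No section plans separate tests at 0.05, so no such figure is charged to the plan.

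**Conclusion.** The Statistical analysis section is wrong as written. Its only named test needs two groups, the study has one, and no paired or one-sample method is named. This rests on the text and needs no assumption.

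The binary primary outcome remains computable, but it has no planned interval and its source and time are open. The chance of counting as improved with no true change is about 8% to 16% at one fixed week, 10% to 25% at week 4 or 8, and 15% to 48% over seven diary weeks, the last only under the any-time reading. These ranges depend on the assumed SDs, correlations, normality and scale. The exact intervals depend only on the counts. Both defects should be corrected before the data are analysed.

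**What to change.** 1. Delete the wording that contrasts treatment groups in Statistical analysis and the reference to two groups in Standard treatment recommendations.
2. Keep the binary fall of at least 1 point in total GCSI as the primary outcome. Tie it to the principal objective: GCSI-DD at week 8 against the one-week screening diary. State how nightly entries become a score, and count a missing week 8 score as not improved. Rewrite the unclear sentence to match.
3. Report the proportion among all treated patients with an exact (Clopper-Pearson) 95% interval.
4. Replace the rank-sum test with the Wilcoxon signed-rank test on each patient's change from baseline. Report the Hodges-Lehmann estimate with its 95% interval, labelled as a supporting secondary analysis. Say how missing changes are handled there.
5. Label PAGI-SYM and the other weeks secondary, and correct the primary comparison line in Sample size justification.
6. Separately, reconcile the statements on 8 weeks of treatment plus 4 weeks of washout, a 12-week course, and post-treatment follow-up at week 16. They decide whether week 12 is on treatment. This review does not say which is right; if the objective changes as a result, item 2 must follow it.

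The cost is wording in the protocol and SAP, with no added patients or visits. The screening diary is already issued, and the diary is already collected at week 8. Diary cover for the fourth treatment week is uncertain, because three weeks' supply is issued for a four-week interval, but a week 8 outcome does not depend on it.
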